5.2. Secondary Efficacy Endpoints

1. Subject-level positive predictive value (PPV) and negative predictive value (NPV) of ¹⁸F-fluciclovine PET for detecting recurrent brain metastases.
2. Lesion-level PPA, NPA, PPV and NPV of ¹⁸F-fluciclovine PET for detecting recurrent brain metastases.
3. Sub-group analyses of subject-level PPA, NPA, PPV and NPV of ¹⁸F-fluciclovine PET, according to primary tumor type and concurrent immunotherapy.
4. Clinical usefulness:
 - a. Number of days taken by the site to establish presence/absence of metastasis by clinical follow-up.
 - b. Proportion of subjects with additional metastases identified on ¹⁸F-fluciclovine PET in addition to standard of care brain MRI.
 - c. Proportion of subjects whose prospective diagnostic management plan changes following ¹⁸F-fluciclovine PET.
5. Inter-reader and intra-reader agreement statistics (kappa coefficient).
6. Treatment-emergent adverse events following ¹⁸F-fluciclovine injection in the subject population.

5.3. Safety Evaluations

Safety will be assessed from the time of ¹⁸F-fluciclovine administration until 1 day post-¹⁸F-fluciclovine administration based on reported serious and non-serious AEs (SAEs and AEs, respectively).

6. SUBJECT SELECTION

6.1. Study Population

Subjects with solid tumor brain metastases previously treated with radiation therapy who meet the inclusion and exclusion criteria will be eligible for participation in this study.

6.2. Inclusion Criteria

1. Male or female ≥ 18 years of age at Screening (Visit 1).
2. Eastern Cooperative Oncology Group (ECOG) performance status of 0-2.
3. Subject or subject's Legally Authorized Representative (LAR) is willing and able to provide written informed consent.
4. Previous history of solid tumor brain metastasis of any origin.
5. Histopathological confirmation of the primary solid tumor or a metastatic site within 4 years of Screening (Visit 1). Cancer of unknown primary is excluded.
6. Previous radiation therapy of brain metastatic lesion(s) completed at least 8 weeks before Screening. Form of radiotherapy may include stereotactic radiosurgery or whole brain radiotherapy, previously delivered as primary (initial) treatment, in the adjuvant setting (e.g., post-surgery), salvage setting (repeat radiation therapy), in or out of the context of previous or concurrent systemic treatments.
7. A reference lesion considered by the site investigator to be equivocal for recurrent brain metastasis, as determined by a recent^{*} SoC MRI brain scan^{**}, measuring ≥ 5 mm in longest diameter on contrast-enhanced MRI, and meeting one of the following radiological criteria:
 - a. $\geq 20\%$ increase in the longest diameter of the reference lesion on contrast-enhanced MRI relative to nadir^{***}, where the longest diameter at nadir is ≥ 10 mm
 - b. ≥ 3 mm increase in the longest diameter of the reference lesion on contrast-enhanced MRI relative to nadir, where the longest diameter at nadir is < 10 mm
 - c. a contrast enhancing lesion at site of previous radiotherapy following complete lesion response (CLR, defined as disappearance of the irradiated contrast enhancing lesion on contrast-enhanced MRI).

^{*}SoC MRI brain scan must be completed within no more than 42 days before study PET scan.

^{**}The SoC MRI brain scan must consist of conventional sequences, defined as:

- T_1 -weighted without and with contrast enhancement, and
- FLAIR and/or T_2 -weighted.

If SoC also includes advanced/investigational MRI sequences, including but not limited to perfusion, spectroscopy, diffusion weighted imaging, and susceptibility weighted imaging, trial entry is permitted as long as the other inclusion criteria are met.

***Nadir is defined as the smallest size after radiotherapy, measured by single longest diameter on an available contrast-enhanced MRI.

8. Subject requires further confirmatory diagnostic procedures to confirm brain MRI findings and is planned for:
 - a. Biopsy or neurosurgical intervention (i.e., craniotomy, laser interstitial thermal therapy where peri-procedural biopsy is planned) as SoC, or
 - b. Clinical follow-up as SoC.
9. Females of child-bearing potential (CBP) to have negative pregnancy test (urine) before on-study ¹⁸F-fluciclovine PET scan.

Note: Women of CBP are defined as sexually mature women without prior hysterectomy or who have had any evidence of menses in the past 12 months. However, women who have been amenorrheic for 12 or more months are still considered to be of childbearing potential if the amenorrhea is possibly due to prior chemotherapy, anti-estrogens, or ovarian suppression.

10. All subjects, male and female, who are not surgically sterilized or postmenopausal as defined above, must agree to abstain from sexual conduct for 24 hours post-¹⁸F-fluciclovine injection.

6.3. Exclusion Criteria

1. Pregnant or breastfeeding during participation in the study, or, where applicable, unwilling to abstain from sexual conduct for 24 hours post-¹⁸F-fluciclovine injection.
2. Subjects with any medical condition or circumstance that the investigator believes may confound the data collected.
3. Subjects with active hematological malignancy or cancer of unknown primary.
4. Subject has received, or is scheduled to receive, another IMP from 1 month or within 5 half-lives of the other IMP (whichever is shorter) before ¹⁸F-fluciclovine injection to the completion of Visit 3.*

**Subjects receiving concurrent systemic therapies, including immunotherapies, are permitted for study entry as long as the concurrent therapy is not an IMP.*

5. Known contraindications to a contrast-enhanced MRI procedure.

7. CONCURRENT MEDICATIONS

All concurrent medications are allowed except for treatments noted in the exclusion criteria ([Section 6.3](#)) and as noted in the prohibited medications section below.

7.1. Allowed Medications and Treatments

Standard therapy for solid tumor brain metastases (e.g., systemic therapies, including immunotherapies) is allowed except for treatments noted in the exclusion criteria described above and as noted in the prohibited medications section below.

7.2. Prohibited Medications and Treatments

The following medications are prohibited during the study and administration will be considered a protocol violation:

- any concurrent therapy that is an IMP, prohibited from 1 month or within 5 half-lives of the other IMP (whichever is shorter) before ¹⁸F-fluciclovine injection to the completion of Visit 3.

8. STUDY TREATMENTS

8.1. Method of Assigning Subjects to Treatment Groups

Not applicable. All subjects will receive a single dose of ¹⁸F-fluciclovine.

8.2. Blinding

Not applicable.

8.3. Formulation of Test Product

¹⁸F-fluciclovine injection is a fluorine-18 labelled synthetic amino acid PET diagnostic agent supplied as a ready-to-inject solution. [REDACTED]

¹⁸F-fluciclovine injection is manufactured by automated radiosynthesis followed by formulation with buffer and aseptic dispensing in a remotely controlled system.

The radioactive isotope Fluorine-18 (¹⁸F) decays by positron emission (β^+ decay, 96.7%) and orbital electron capture (3.3%) with a half-life of approximately 110 minutes.

8.4. Packaging and Labelling

The investigational agent is supplied as a unit dose for injection in a syringe with a radioactive concentration at a reference date and time that is stated on the container label. Each syringe is supplied in a container providing appropriate radiation shielding. Information will be provided with the shipment giving the confirmation number, radioactive concentration of injection (mCi/mL) at a stated time and date, shelf life information, protocol number and a unique prescription number. The radiochemical purity of ¹⁸F-fluciclovine injection is not less than 95% during the shelf life of the product.

8.5. Supply of Study Drug at the Site

Sites will be provided with instructions for ordering the ¹⁸F-fluciclovine doses for use in the study. The specific date and time for a subject to be scanned needs to be included when placing the order. The site should be aware that next-day delivery of the ¹⁸F-fluciclovine may not be feasible in all circumstances. If a site intends to administer the ¹⁸F-fluciclovine dose the day after ordering, they should first confirm the order and delivery time with the study IMP administrators. The ¹⁸F-fluciclovine will be delivered from the radiopharmacy to the imaging site by courier. Each syringe is supplied in a container providing appropriate radiation shielding. The site must keep records of all shipments of ¹⁸F-fluciclovine received, dispensing and disposal/destruction performed on site as is appropriate to each facility.

Additional details concerning ordering and handling of the IMP are provided in the Pharmacy Manual and Imaging Acquisition Standards.

8.6. Dosage/Dosage Regimen

Subjects will receive a single dose of ¹⁸F-fluciclovine by injection, 185 MBq (5 mCi) \pm 20%, delivered as an IV bolus by site staff.

8.7. Dispensing

When the study site receives the dose, both prior to and after administration, the activity in the syringe will be measured using an appropriate dose calibrator. Should the activity be less than 148 MBq (4 mCi) or the volume required exceed 5 mL of undiluted material or the administration be after the labeled expiration time, the scan should not be performed.

Additional details for handling the IMP are provided in the Pharmacy Manual.

8.8. Administration Instructions

Position the subject supine, with arms alongside the body and the head stabilized appropriately. The entire brain, including the cerebellum, should be in the field of view. A venous cannula will be inserted, and the subject will receive an administered activity of 185 MBq (5 mCi) \pm 20% of ^{18}F -fluciclovine. The ^{18}F -fluciclovine will be administered as an IV bolus injection followed by a 10 mL flush of normal saline solution.

Additional details are provided in the Imaging Acquisition Standards.

8.9. Storage

The shelf-life of ^{18}F -fluciclovine injection is up to 10 hours from the end of production and the product must not be administered beyond this limit. ^{18}F -fluciclovine should be stored at 15 to 25°C in a shielded container.

All non-radioactive containers (shielding, transport cans) must be returned to the manufacturing site. Shipping containers that are radioactive must be decontaminated or allowed to decay prior to return to the manufacturing site. Used product syringes and other radioactive materials must be destroyed at either the study site or another designated facility.

Waste must be disposed of according to national and local regulations for radioactive material.

Precautions for the safe handling of radioactive materials should be observed.

Additional details are provided in the Pharmacy Manual.

8.10. Study Drug Accountability

An accurate and current accounting of the dispensing and disposal of study drug for each subject will be recorded on the Investigational Drug Accountability Record. These records will be maintained at the radiopharmacy, hot lab or nuclear medicine department responsible for receipt and dispensation of study drug. Records should include at a minimum:

- Dates of receipt, lot number and quantities received from Sponsor or designee;
- Dates, subject numbers, and amount of ^{18}F -fluciclovine dispensed for administration to specific subjects, including administered dose activity;
- If applicable, for any unused IMP, dates, lot numbers, and reason dose was not administered.

The investigator is responsible for ensuring that study drug is administered only to subjects included in this study in accordance with the study protocol.

Throughout the study, drug accountability will be performed by appropriate Sponsor representative(s) and when appropriate, reconciliation will be performed. Additional details are provided in the Pharmacy Manual.

8.11. Measures of Treatment Compliance

Not Applicable. This is a single dose study, administered by site staff.

8.12. End Of Trial

Subjects will be followed to 6 months per SoC. Month-6 Follow-up data abstraction (6 months following ¹⁸F-fluciclovine PET) will be conducted in order to collect diagnostic, treatment, and response information which will be provided to a CTP for review. Subjects whose reference or other equivocal lesion(s) continue to be considered equivocal at site level at Visit 5 / Month 6 will undergo a study MRI.

9. STUDY PROCEDURES AND GUIDELINES

A schedule of events representing the required study procedures to be performed for the duration of the study is provided in [Table 1](#).

Prior to conducting any study-related activities, written informed consent (and assent, if applicable) including Health Insurance Portability and Accountability Act (HIPAA) authorization must be signed and dated by the subject or LAR ([Section 17.3](#)).

Table 1. Schedule of Study Procedures

	Day -42 to -1 SoC MRI	Visit 1 Day -28 to -1 Screening	Visit 2 Day 1 IMP + PET	Visit 2 Day 1 to 4 On-Study MRI	Visit 3 Day 2 to 4 Safety Follow-Up Phone Call	Visit 4 Day 2 to 22 SoC Biopsy / Neurosurgical Intervention (if applicable)	Visit 5 Month 6 (183 days ± 14 days) Follow-up
SoC MRI					1 to 3 days after ¹⁸ F-fluciclovine injection, before optional SoC Biopsy / Neurosurgical Intervention (if applicable)	If applicable, at time of pre-planned SoC Biopsy / Neurosurgical Intervention and after Visit 2 MRI and Visit 3 Follow-Up	Through 6 months after ¹⁸ F-fluciclovine PET
Before Visit 1 Screening		Within 28 to 1 day before Visit 2 Day 1	Within 28 to 1 day before Visit 2 Day 1	Neurosurgical Intervention Visit 4 Day 3			
Informed Consent	X						
Confirm inclusion/exclusion criteria		X		X			
Demographics ^a	X						
Baseline Characteristics ^b				X			
Medical / Disease History ^c				X			
ECOG Performance Status ^d				X			
Concomitant Medications				X		X	
Vital Signs ^e				X		X	
Pregnancy Test (Urine) ^f				X		X	
Diagnostic Management Plan				X		X	
Order ¹⁸ F-fluciclovine dose				X			
Eligibility Review ^g				X			
¹⁸ F-fluciclovine Injection					X		
Dynamic PET Brain Scan					X		
Adverse Events					X		
On-Study MRI Brain Scan					X		X ^h
Annotate Reference Lesion on SoC MRI Brain Scan				X			
Annotate other equivocal lesions (if applicable) ⁱ				X			

Table 1. Schedule of Study Procedures

	Day -42 to -1 SoC MRI	Visit 1 Day -28 to -1 Screening	Visit 2 Day 1 IMP + PET	Visit 2 Day 1 to 4 On-Study MRI	Visit 3 Day 2 to 4 Safety Follow-Up Phone Call	Visit 4 Day 2 to 22 SoC Biopsy / Neurosurgical Intervention (if applicable)	Visit 5 Month 6 (183 days ± 14 days) Follow-up
Identify and annotate additional PET lesions (i.e. potential additional lesions not previously reported on SoC MRI [if applicable]) ^j			1 to 21 days before SoC optional Biopsy / Neurosurgical Intervention Visit 4 Day 3		1 to 3 days after ¹⁸ F-fluciclovine injection, before optional SoC Biopsy / ¹⁸ F-fluciclovine injection or up to 3 days after	If applicable, at time of pre-planned SoC Biopsy / Neurosurgical Intervention and after Visit 2 MRI and Visit 3 Follow-Up	Through 6 months after ¹⁸ F-fluciclovine PET
Safety Follow-up Phone Call					X		
SoC Biopsy/Neurosurgical Intervention						X	
Document Neurosurgical Procedure						X	
Record local histopathology results and send specimens to central histopathology laboratory						X	
Neurological Deterioration Assessment						X	
Clinical Follow-Up / Data abstraction ^k							X

ECOG, Eastern Cooperative Oncology Group; IMP, investigational medicinal product; MRI, magnetic resonance imaging; PET, positron emission tomography; SoC, standard of care.

^a Demographic information recorded at Screening will include age, sex, race and ethnicity.

^b Baseline assessments will include pre-scan body weight and height. Pre-scan body weight and height will be collected at Visit 2.

^c Treatment history for previous cancer to include previous treatments for brain metastases and previous cancer treatments for primary tumor. Any changes to the subject's medical condition between Screening (Visit 1) and the start of ¹⁸F-fluciclovine administration (Visit 2) should be recorded as updated medical history.

^d A standard of care ECOG assessment may be recorded as the Screening ECOG if the assessment was performed within 28 days of Screening.

BED-FLC-312 Protocol Version 3.0, 17 March 2023

Page 41 of 73

^e Vital signs (body temperature, blood pressure, pulse and respirations) will be collected after resting for at least 5 minutes before IMP injection, and after resting for at least 5 minutes following PET scan.

^f Females of childbearing potential.

^g Eligibility review to include collection and review of prior post-treatment MRI brain scans as needed to confirm eligibility. Prior post-treatment MRI brain scans and

^h current SoC MRI images to be uploaded to central imaging core lab.

ⁱ A study MRI will be performed for any subject whose reference or other equivocal lesion(s) is/are still considered equivocal at site level at Visit 5 / Month 6 unless a SoC MRI was performed within the preceding 3 weeks.

^j If $f > 1$ equivocal lesion is under evaluation as SoC, the on-site investigator will also annotate 'other equivocal lesions' on the Visit 2 On-Study MRI brain scan, defined as follows:

a) Equivocal for recurrent metastasis on SoC MRI (according to the same radiological criteria for a reference lesion per inclusion criterion #7).

b) Where SoC biopsy/neurosurgical intervention procedure is planned, these are the other equivocal lesions pre-planned for biopsy/intervention.

c) Where SoC clinical follow-up is planned, these are the other equivocal lesions pre-planned for SoC clinical follow-up.

^k Additional PET lesions are potential additional lesions identified by the on-site investigator on ¹⁸F-Fluciclovine PET scan, not previously reported on SoC MRI, and judged to be suggestive of brain metastasis, warranting confirmation by clinical follow-up, biopsy or resection according to SoC.

^l Relevant clinical and imaging data will be uploaded for up to 6 months following ¹⁸F-fluciclovine PET scan.

9.1. Clinical Assessments

9.1.1. Concomitant Medications

All concomitant medication and concurrent therapies will be documented at Screening (Visit 1), at IMP administration (Visit 2) and at the post-treatment Safety Follow-up phone call (Visit 3), and at early termination when applicable. In addition to recording all concomitant medications as described, treatments and therapies for the brain lesion(s) and primary tumor will be recorded through Month 6 (Visit 5) as described in [Section 9.1.8](#). Dose, route, frequency of administration, and indication for administration and dates of medication will be captured.

9.1.2. Demographic and Baseline Characteristics

Demographic information recorded at Screening will include age, sex, race and ethnicity. Baseline assessments of pre-scan body weight and height will be collected at Visit 2.

9.1.3. ECOG Performance Status

Conduct ECOG Performance Status assessment at Screening (Visit 1) or record a standard of care ECOG Performance Status if the assessment was performed within 28 days prior to Screening (Visit 1) (see [Appendix 1](#)).

9.1.4. Medical History

Record medical and disease history at Screening (Visit 1). Include history for previous brain metastases and brain metastases treatments, diagnosis of primary tumor and previous cancer treatments for primary tumor, and any other previous cancers, as applicable. Brain metastases and primary tumor histories should include dates of initial diagnosis, initial tumor stage, dates and type of definitive therapy and adjuvant treatment (if given). Any changes to the subject's medical condition between Screening (Visit 1) and the start of ¹⁸F-fluciclovine administration (Visit 2) should be recorded as updated medical history.

9.1.5. Imaging Studies

Sites will be instructed to submit historic SoC imaging data required to confirm eligibility. Submitted MRI scans should confirm the reference lesion criteria outlined in [Section 6.2](#). Therefore, these should be the MRI scan confirming nadir or showing complete response, the current SoC MRI brain scan performed before Screening (Visit 1), and may include the pre-treatment MRI if available. Sites will annotate and measure the reference lesion and other equivocal lesions on the current SoC MRI brain scan using the imaging core lab study imaging platform.

The reference lesion is defined as the lesion which is:

- a. Equivocal for recurrent metastasis on SoC MRI (according to inclusion criterion #7, see [Section 6.2](#)).
- b. Intended for SoC biopsy/neurosurgical intervention procedure (if planned). If >1 lesion is intended for biopsy/intervention, the largest of these lesions will be the reference lesion.
- c. Where clinical follow-up is planned, the largest of all equivocal lesions (if >1 is present) will be the reference lesion.

If >1 equivocal lesion is under evaluation as SoC, the on-site investigator will also annotate ‘other equivocal lesions’ on the pre-study SoC MRI brain scan, defined as follows:

- a. Equivocal for recurrent metastasis on SoC MRI (according to the same radiological criteria for a reference lesion per inclusion criterion #7, see [Section 6.2](#)).
- b. Where SoC biopsy/neurosurgical intervention procedure is planned, these are the other equivocal lesions pre-planned for biopsy/intervention.
- c. Where SoC clinical follow-up is planned, these are the other equivocal lesions pre-planned for SoC clinical follow-up.

Sites will perform and upload a ¹⁸F-fluciclovine PET brain scan on Day 1 (Visit 2), and an on-study MRI brain scan performed 0 to 3 days after the ¹⁸F-fluciclovine PET scan (Visit 2).

The site investigator will review the ¹⁸F-fluciclovine PET scan to identify potential additional lesions, not previously reported on SoC MRI (termed ‘additional PET lesions’). Additional PET lesions should be annotated only where judged suggestive of brain metastasis, warranting confirmation by clinical follow-up, biopsy or resection, according to SoC practice. Moreover, an additional PET lesion should be discrete and spatially separate from known, pre-existing lesions. In particular, the following should not be annotated as Additional PET lesions: known pre-existing non-progressive lesions (considered at site level as stable or partially responding), ¹⁸F-fluciclovine activity contiguous with a known lesion (previously annotated or otherwise) and apparently incongruent with the lesion’s outline on correlating MRI, particularly where this may be reasonably explained by image registration.

The investigator will then annotate the additional PET lesions on the ¹⁸F-fluciclovine PET scan using the imaging core lab study imaging platform. The site investigator will also confirm the sites of the reference and other equivocal lesions on the Visit 2 scans.

For each annotated lesion, a lesion identifier will be automatically created and assigned by the imaging core lab study imaging platform. For each annotated lesion, the site will also be required to define the anatomical location.

Subjects whose reference or other equivocal lesion(s) continue to be considered at the site-level to be equivocal for brain metastasis at Month 6 (Visit 5) will have a final research MRI unless an SoC MRI was performed within the prior 3 weeks.

9.1.5.1. ¹⁸F-fluciclovine PET Scan

Dynamic PET/CT or PET/MRI scan of the brain to be performed at Visit 2 following ¹⁸F-fluciclovine injection. If the PET scan is performed on a PET/CT scanner, a CT scan of the brain will also be performed for attenuation correction. Site investigator will review the ¹⁸F-fluciclovine PET scan to identify potential additional PET lesions (this will be done with the Visit 2 MRI scan for anatomical reference). The PET scan will be uploaded to the central imaging core laboratory by the site investigator/site staff. The selected PET scanner must be qualified by the study management team prior to any imaging studies. Full details on the imaging protocol are provided in the Imaging Acquisition Standards.

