9.1.5.2. On-Study MRI

Throughout this study, ¹⁸F-fluciclovine PET will be read with standard MRI for anatomical reference. Therefore, all subjects will receive an on-study, study-specific brain MRI scan at Visit 2, ideally on the same day as the PET scan or ≤ 3 days after the PET scan. The on-study MRI will consist of MRI sequences per the minimum standard consensus recommendations

for a standardized brain tumor imaging protocol for clinical trials in brain metastases (BTIP-BM) ([Kaufmann, 2020](#)).

These will include:

- T₁-weighted MRI without and with contrast enhancement,
- FLAIR and/or T₂-weighted MRI, and
- Diffusion-weighted imaging.

On-study MRI brain scans will be uploaded to the central imaging core laboratory by the site investigator/site staff. In addition to reviewing the ¹⁸F-fluciclovine PET scan to identify potential additional PET lesions, on the Visit 2 MRI, the site investigator will confirm the sites of the reference and other equivocal lesions initially defined on the SoC MRI. Full details on the imaging protocol are provided in the Imaging Acquisition Standards. If available, scans acquired on a PET/MRI are allowed.

A final on-study MRI will be performed at Visit 5 (Month 6) only for any surviving subject whose reference or other equivocal lesion(s) remain equivocal at site level, unless an SoC MRI was performed within the preceding 3 weeks.

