Visit 2 on-study MRI brain scan should take place on the same day as the ¹⁸F-fluciclovine PET scan (Day 1) or up to 3 days after. Where applicable, it should take place before the Visit 4 – SoC biopsy/neurosurgical intervention.

1. Perform Visit 2 on-study MRI brain scan as outlined in [Section 11.5](#).

2. Upload Visit 2 on-study MRI brain scan to the central imaging core laboratory.
3. Review of ¹⁸F-fluciclovine PET brain scan (with Visit 2 MRI for anatomical reference) by site investigator to identify potential additional PET lesions, not previously reported on SoC MRI.
4. Confirm sites of reference lesion and other equivocal lesions on Visit 2 scans.

The on-site investigator will review the ¹⁸F-fluciclovine PET scan to identify and annotate potential additional lesions, not previously reported on SoC MRI (termed ‘additional PET lesions’). Additional PET lesions should be annotated only where judged suggestive of brain metastasis, warranting confirmation by clinical follow-up, biopsy or resection, according to SoC practice. Undertaking biopsy/resection of additional PET lesion(s) identified on the ¹⁸F-fluciclovine PET scan is at the discretion of on-site investigators. Moreover, an additional PET lesion should be discrete and spatially separate from known, pre-existing lesions. In particular, the following should not be annotated as Additional PET lesions: known pre-existing non-progressive lesions (considered at site level as stable or partially responding), ¹⁸F-fluciclovine activity contiguous with a known lesion (previously annotated or otherwise) and apparently incongruent with the lesion’s outline on correlating MRI, particularly where this may be reasonably explained by image registration.

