11.8.3. Blinded Image Evaluation

A 3-reader central, independent BIE of the ¹⁸F-fluciclovine PET scans will be performed, diagnosing recurrent metastasis (positive) vs no recurrent metastasis (negative) for each reference lesion, other equivocal lesion(s) and additional PET lesion(s), using the Visit 2 MRI for anatomical reference.

- Image criteria used in the BIE will be informed by a Phase 2b study (BED-FLC-219).
- Inter- and intra-reader concordance will be measured.
- The readers will not have access to clinical history, prior clinical imaging, any site-generated diagnostic evidence, nor the final patient outcome.

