15.1. Estimation of Sample Size

Approximately 150 subjects will be enrolled, to obtain 130 evaluable subjects.

A one-sample binomial exact test will be used to test the following hypotheses in NPA and PPA of ¹⁸F-fluciclovine PET:

NPA

- $H_0(\text{NPA})$: NPA of PET $\leq \text{NPA}_0$
- $H_1(\text{NPA})$: NPA of PET $> \text{NPA}_0$

PPA

- $H_0(\text{PPA})$: PPA of PET $\leq \text{PPA}_0$
- $H_1(\text{PPA})$: PPA of PET $> \text{PPA}_0$

Where NPA_0 and PPA_0 are performance goals for NPA and PPA, respectively.

Performance goals of 50% (NPA_0) for NPA and 50% (PPA_0) for PPA were selected as acceptable thresholds given the setting where SoC imaging is already equivocal. The lower limits for the exact 95% confidence intervals (CI) (Clopper-Pearson method) for both NPA and PPA should be greater than 50%. Assuming an NPA of at least 70% and a PPA of at least 70% for ¹⁸F-fluciclovine PET would need to be observed, a sample size of 130 would achieve 90% power at a 1-sided significance level of 0.025 to reject the performance goals for both NPA and PPA; assuming a brain metastasis prevalence rate of 0.5.

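### The reference lesion's site on the Visit 2 scans is confirmed after the site has reviewed the PET, and the documents do not say which lesion mark the blinded readers receive

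*Protocol*

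**What the plan says.** At Screening the site annotates and measures the reference lesion on the SoC MRI in the core lab's imaging platform (Protocol 9.1.5 and 10.1). This is before any PET. The lesion is fixed by inclusion criterion 7 and by a rule based on the planned biopsy target or the largest lesion.

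At Visit 2 the position is confirmed again, and three places describe this differently:

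- Section 9.1.5, after describing the PET review for additional lesions: "The site investigator will also confirm the sites of the reference and other equivocal lesions on the Visit 2 scans".
- Section 10.3, as item 4, directly after the PET review in item 3: "Confirm sites of reference lesion and other equivocal lesions on Visit 2 scans".
- Section 9.1.5.2, which places the step on the Visit 2 MRI: "the site investigator will confirm the sites of the reference and other equivocal lesions initially defined on the SoC MRI".

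The blinded readers diagnose each reference lesion using the Visit 2 MRI for anatomy. Section 11.8.3 limits what else they see: "The readers will not have access to clinical history, prior clinical imaging, any site-generated diagnostic evidence, nor the final patient outcome". The central neuroradiologist in 11.8.4 looks at the historical and Screening SoC MRI only, and the related sensitivity analysis in SAP 7.4.5.1 concerns whether the lesion was equivocal at baseline.

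**The concern.** The reading target for the primary endpoint should be fixed without knowledge of the index test. Here the investigator who confirms where the reference lesion lies on the Visit 2 scans has, in the order listed in 10.3, just looked at the PET. Nothing requires the confirmation to come first or to be made without the PET.

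The SoC MRI carrying the pre-PET mark is withheld from the readers, so something must direct them to the lesion on the Visit 2 images. The site's confirmation is the only step described that could do so. Up to 45 days may separate the two MRIs (42 days from SoC MRI to PET, plus 3 days from PET to Visit 2 MRI).

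Section 9.1.5 itself foresees tracer activity that adjoins a known lesion but does not match its MRI outline. It bars calling this an additional lesion, but does not say whether it counts toward the reference lesion. That is where a mark could drift.

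A mark drawn toward uptake turns negative reads positive. In truly recurrent lesions this raises PPA; in non-recurrent lesions it lowers NPA. All three readers would work from the same mark, so the requirement that the same two of three readers succeed gives no protection.

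**Working it through.** **Inputs (Protocol 15.1 and 15.5).** 130 evaluable subjects and "assuming a brain metastasis prevalence rate of 0.5", hence 65 per class. Goals of 50% for each measure; planned PPA and NPA of 70%; one-sided 0.025 exact binomial test. Success needs both goals in the same two readers.

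**Reproducing the plan's figure.** The plan states that "a sample size of 130 would achieve 90% power at a 1-sided significance level of 0.025". With n = 65, 41 correct reads (63.1%) is the smallest passing count: the Clopper-Pearson lower limit is 0.502 at 41/65 and 0.486 at 40/65. The exact one-sided level is 0.0232. Write the pass probability as

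π(p) = Σ (x = 41 to 65) C(65, x) pˣ (1 − p)⁶⁵⁻ˣ

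Then π(0.70) = 0.910. The 90% therefore reproduces for each endpoint taken singly. For both endpoints in one reader, treated as independent, the baseline is 0.910 × 0.910 = 0.828.

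**Illustrative shift.** The documents give no rate of displaced marks, so the number k of reads per class that turn positive is an assumption, taken as 1 to 3 of 65 (1.5 to 4.6 points). The reference standard is assumed unchanged.

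- PPA′ = PPA + k/65 and NPA′ = NPA − k/65
- Joint pass chance, one reader = π(PPA′) × π(NPA′)

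Products are taken before rounding.

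| True PPA / NPA | k = 0 | k = 1 | k = 2 | k = 3 |
|---|---|---|---|---|
| 70% / 70% | 0.910 × 0.910 = 0.828 | 0.948 × 0.857 = 0.812 | 0.972 × 0.787 = 0.765 | 0.986 × 0.702 = 0.693 |
| 60% / 70% | 0.355 × 0.910 = 0.323 | 0.453 × 0.857 = 0.388 | 0.555 × 0.787 = 0.437 | 0.655 × 0.702 = 0.460 |
| 60% / 60% | 0.355 × 0.355 = 0.126 | 0.453 × 0.266 = 0.121 | 0.555 × 0.191 = 0.106 | 0.655 × 0.130 = 0.085 |

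**Two further cases.**

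- If marks drift only in truly recurrent lesions, NPA is untouched. At 70%/70% the joint figure then rises to 0.948 × 0.910 = 0.862 (k = 1) and 0.986 × 0.910 = 0.898 (k = 3).
- If true PPA is 50%, the chance of wrongly passing the PPA goal alone goes from 0.023 to 0.041 (k = 1) and 0.106 (k = 3).

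**Reading the sections together.** The pre-PET mark is on a scan the readers do not have. The only later positional step is not masked to PET. The only independent check of the reference lesion is made on scans that predate Visit 2. No section closes the gap between them.

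**The case against.** The strongest reply is that the target is already fixed. The lesion is annotated and measured before PET in the core lab's platform, which gives each annotated lesion an identifier. Visit 2 only confirms it, no section permits moving it, and 9.1.5.2 names the MRI. Withholding prior imaging from readers does not stop the core lab from carrying a coordinate across, and the Imaging Acquisition Standards, which are not available here, may already require that. Only the numbered list in 10.3 implies an order; 9.1.5 has no numbered steps.

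Most of this stands, and it limits the point. A reader might infer that the reference lesion is first located after PET. It is not. A reader might also infer that the readers demonstrably read the site's PET-informed location. That is plausible, because Protocol 15.6.5 speaks of lesions the site has defined, but no section says which mark is displayed. The prior annotation confines the realistic risk to small drift at or beside a known lesion.

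What the reply does not remove is the listed order in 10.3, the lack of any masking of the confirmation to PET, and the absence of a check on the Visit 2 position. Whether the SoC mark is carried over is a matter the protocol should state.

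**Conclusion.** The point holds as a gap in how the reading target is protected. The plan lists an unmasked confirmation of the primary-endpoint target after PET review, and leaves open which mark the blinded readers receive. If they receive the Visit 2 confirmation, any drift toward uptake biases PPA upward and NPA downward, in common across readers.

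Its size cannot be estimated from the documents. Under the assumed shift of 1 to 3 reads per class, with 65 per class and independent endpoints, one-reader joint power at the planning values falls by 1.6 to 13.5 percentage points (0.828 to 0.812-0.693). Where PPA is the weaker measure (60% against NPA 70%), the joint pass chance rises by 6.5 to 13.7 points (0.323 to 0.388-0.460).

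It is tempting to conclude that the arrangement makes the trial easier to pass. The two-part success rule does not support that in general: a shift unrelated to true status lowers the chance of success at 70%/70% and at 60%/60%. It helps where PPA is the weaker limb, or where drift is concentrated in truly recurrent lesions. Looking at the PPA goal alone (0.355 rising to 0.453-0.655 at a true PPA of 60%) would mislead.

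**What to change.** - In Protocol 9.1.5 and 10.3, have the site confirm and lock the reference and other equivocal sites on the Visit 2 MRI alone, before the PET is opened. Alternatively, have the core lab transfer the SoC MRI mark to the Visit 2 MRI. The PET is then reviewed for additional PET lesions.
- In 11.8.3, state that this locked mark is the one shown to the blinded readers, and that any later change is logged and not passed to them.
- Reconcile the wording of 9.1.5 and 10.3, which refer to the Visit 2 scans in general, with 9.1.5.2, which refers to the Visit 2 MRI.

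The cost is a change in step order in the protocol and on the imaging platform, with no extra scan, visit or reader. The site's PET review already uses the Visit 2 MRI (9.1.5.1 and 10.2), so confirming the sites on that MRI first need not delay it. If the core lab already transfers the SoC mark, a sentence in 11.8.3 saying so resolves the question of what the readers receive.
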